#### Neuroimaging:

At Yellow Visit 2, participants will either undergo neuroimaging (i.e., task fMRI, resting-state MRI, structural MRI, DWI) or complete replacement tasks at home. For the self-affirmation intervention, all participants will be shown a series of eight core values (i.e., money, creativity, religion, politics, family & friends, sense of humor, independence, spontaneity) and will be asked to choose the values they think are most and least important to them as per Cascio et al. (2016). They will proceed to fill out a simple activity sheet of questions about the value they chose (both intervention and control group versions attached). The questions will be designed to help them practice the thorough reflection required for the scanner self-affirmation task. Each participant's vision will be assessed using a Snellen chart so they can be fitted with appropriate, MRI-safe

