corrective eyewear if necessary. The randomization scheme will be prepared by the Harvard Catalyst Biostatistical Group using a permuted block method with random blocks. The randomization ratio will be 1:1. Sealed envelopes will be provided to the investigator and stored at the designated site. All participants will perform an fMRI task with a block design containing a self-affirmation manipulation followed by either gain- or loss-framed persuasive messaging about physical activity. Participants in the intervention group will be asked to think about situations that allow them to reflect on their highest ranked value before being presented with gain-framed health messaging, whereas participants in the control group will reflect on their lowest ranked value before receiving loss-framed health messages. During the self-affirmation block, participants will be presented with prompts about value-relevant topics to allow them to elaborate upon and connect with situations that are pertinent to their core value (e.g., if religion was the highest ranked value, an example self-affirmation statement would be, 'Think of a time in the future when you would be inspired by religion' or 'Think of a time in the future when you would feel grateful for religion'). All statements will focus on the self rather than relying on factual knowledge to ensure that topic importance rather than topic knowledge differentiates high- and low-ranked values. As a within-subject control condition, participants in both groups will also be shown prompts about value-neutral statements (e.g., 'Think of a time in the future when you would check the weather'). For a detailed description of the self-affirmation manipulation see Cascio et al. (2016) and Falk et al. (2015). Next, participants will undergo exposure to a block of gain-framed persuasive health messages that encourage physical activity, as in Notthoff et al. (2014), or a block of comparably constructed loss-framed persuasive health messages that similarly encourage physical activity. The set of health messages primarily consists of wellness information taken from the Physical Activity Guidelines for Americans published by the U.S. Department of Health and Human Services. The method of balancing gain- and loss-framed messages was inspired by Notthoff et al. (2014). In older adults, gain-framed messages (e.g., 'Walking has important cardiovascular health benefits') have previously been shown to be more effective at encouraging exercise compared to loss-framed messages (e.g., 'Not walking enough can lead to increased risk for cardiovascular disease') (Notthoff et al., 2014).

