#### Daily Messaging:

Over a period of six weeks, all participants will receive daily prompts about their highest- (intervention group) or lowest- (control group) ranked value, followed by gain-framed (intervention group) or loss-framed (control group) messaging about physical activity. The daily self-affirmation and health messages will be a combination of the same 21 messages the participants had seen in the fMRI scanner task mixed with 21 new messages. We expect that only the participants in the self-affirmation + gain-framed messaging group will increase their physical activity from baseline. All participants will also answer questions about their memory of the messages (whether they are old or new), affect, self-efficacy, and implementation intention. This will be delivered via email or text using oTree (Robinson & Lachman, 2016; Lachman et al., 2018; Chen et al., 2015).

We will use the oTree library to distribute survey questions via email or text to participants during the 6-week intervention. oTree is licensed under the MIT open source license and offers use of several libraries and capabilities for psychological research. It was designed specifically for “controlled behavioral experiments in economics, psychology, and related fields” ([www.otree.org](http://www.otree.org)). The messaging system runs on a Heroku server, which is a Cloud application program that allows websites to be hosted online. The messaging system sends out participant-specific, hash-encrypted links. This safety measure prevents participants from guessing other links and accessing other participants’ survey pages. Links will be sent to participants individually through email; however, survey responses will be identified solely by the Participant ID that oTree randomly generates, and will not be connected to names, emails, or any other identifying information. Further, links cannot be used to figure out the email address of the respondent. Only the necessary research staff will have access to the information connecting participants to the links they were sent.

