The data are stored on a Heroku server. Heroku’s privacy policy states that, “We take steps to protect the privacy of our customers and protect data stored within the platform. Some of the protections... include authentication, access controls, data transport encryption, HTTPS support for customer applications, and the ability for customers to encrypt stored data.” Further, answers to survey questions are stored in number form corresponding to the multiple-choice option selected, without a key to the meaning of the choice or the question itself. There is a mandatory Administrator login, requiring a username and password, to gain access to this data. Only necessary research personnel will have the login information.

We will use the Remind app to deliver links to the oTree survey via text to participants every day. Remind is a texting service primarily used by educators, students, and parents that is compliant with federal privacy laws protecting students. It has been awarded the ISO 27001:2013 certification, which is an international standard for information security

management and governance (<https://www.remind.com/blog/iso-27001-certification>). Participants will not discuss personal and/or health information through Remind, and the links sent to them will not contain private information.

Follow-up measures:

After the intervention, participants opting into the MRIs will undergo repeat neuroimaging (i.e., resting state MRI, structural MRI, task fMRI, DWI), physical assessment session, and specified cognitive tests. Additionally, in an attempt to determine the extent of benefits following the end of the formal intervention, participants will be assessed again at 3 months post-intervention, with 7 days of accelerometry recording to determine physical activity, and behavioral and psychosocial measures to assess continued cognitive benefits.

Outcome measures outside of the neuropsychological assessment battery are as follows:

Outcome measure	Type	Timeframe	Brief description
Total step count (average steps/day)	Primary	Week 0 (baseline); Week 3; Week 6; 3 Months	This metric quantifies the change in the average number of steps taken each day, from the baseline, Week 2, Week 6, and 3-month periods. It is a marker of change in habitual ambulatory activity.

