128 The DASH study is a stratified block randomized controlled trial. After reading and signing informed consent, recruited participants are randomized to either a self-affirmation plus gain-framed daily messaging group (intervention) or a loss-framed daily messaging only group (control) with a ratio of 1:1. Due to the constraints of in-person assessment during the COVID-19 pandemic, onsite participation in the MRI scans before and after the intervention is optional. Therefore, we stratify the randomization by MRI participation (yes/no) to ensure the same distribution of MRI and behavioral-only participants across the two groups. Loss-framed messages were chosen as a control group (over neutral messaging) as they provide the same contextual information as the gain-framed messages (only framed in a negative way), compared

139 to neutral messages which contain factual information (see Figure 3B for an example of gain-
140 versus loss-framed messages). All participants are informed about the randomization but blinded
141 to the group assignment. Participants are informed that the study aims to examine whether a 4-
142 week program promotes brain health and behavior. However, it is not possible to blind
143 experimenters, as they view the intervention related materials and give instructions during the
144 assessments. The randomization scheme is prepared by the Harvard Catalyst Biostatistical Group
145 using a stratified permuted block method with random blocks. All experimenters are blinded to
146 the block size. Sealed envelopes are provided to the investigator and stored at the designated site.
147 This trial is registered on clinicaltrials.gov with an identifier NCT04315363. This study received
148 ethical approval from Northeastern University Institutional Review Board (IRB).
149

150 **Participants**

151
152 We plan to recruit 80 sedentary older adults for this study between the ages of 60 and 95
153 years that engage in less than 150 minutes of moderate-to-vigorous-intensity aerobic exercise per
154 week and more than 8 hours of sitting time per day, as assessed with a self-report during an
155 initial phone screening. We plan to recruit a diverse population that is balanced across race, sex,
156 and socioeconomic status. The study is advertised via promotional flyers in and around the
157 Boston area and local senior citizen centers as well as online advertisements through websites

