158 such as Craigslist and Facebook. Potential participants are screened by phone. The Telephone
159 Interview of Cognitive Status (TICS) is used initially to screen cognitive function. Sitting Time
160 questionnaire [27] and International Physical Activity Questionnaire [28] are used for screening
161 physical activity engagement and sedentary behavior. Potential participants are asked a series of
162 questions relating to the inclusion/exclusion criteria and past medical history.
163

164 **Intervention**

165 ***Study timeline***

166 An illustration of the study timeline can be seen in Figure 1. Each participant undergoes a
167 baseline session (T1) one week before the beginning of the intervention. Informed consent is
168 obtained at baseline, during which participants specify whether they opt to participate in the MRI
169 scans or not. Randomization takes place after obtaining informed consent (T1) and participants
170 are assigned into either the intervention or control group. During the T1 visit, the participants
171 also undergo baseline testing including neuropsychological tests and neurobehavioral
172 inventories, which take about 3 hours in total. In order not to prime exercise for the baseline
173 physical activity level, inventories that are related to exercise and self-perception are not
174 administered during T1 visit. At baseline, participants wear an activPAL monitor on their thigh
175 to assess postural aspects of sedentary behavior including time spent sitting and lying and a
176 wrist-worn accelerometer on their non-dominant hand to assess physical activity (see physical
177 activity monitoring). Both monitors are worn for a week. One week later (T2), physical
178 assessments and the remaining neurobehavioral inventories related to exercise and self-
179 perception will be administrated, which takes about 1.5 hours. The intervention lasts 4 weeks,
180 during which participants receive daily intervention messages via email or smartphone.
181 Participants are fitted with the accelerometers again for a one-week mid-intervention period
182 (week 3). The post-intervention visit (T3) is scheduled at the beginning of the last intervention
183 week (week 4). After the last intervention week (T4), participants repeat the neurobehavioral
184 week (week 4). After the last intervention week (T4), participants repeat the neurobehavioral
185 week (week 4). After the last intervention week (T4), participants repeat the neurobehavioral

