[figure not shown]
186 inventories, neuropsychological tests and physical assessments. Three accelerometer calls are
187 administered by two research assistants, for the purpose of giving instructions and answering
188 questions about accelerometers. The estimated overall participation time is 16 hours, which may
189 vary across individuals. To minimize attrition, each assessment session (i.e., T1, T2, T3, T4) is
190 self-paced and has been divided into smaller visits, each of which lasts no longer than 2 hours.
191 During each visit, participants take breaks every 20 minutes to minimize the risk of fatigue.
192

193 ***Daily messaging***

194

195 The 4-week intervention consists of daily messages via email using the online software
196 oTree, an open-source platform for implementing messaging survey, which allows for
197 accessibility via desktop or smartphone [29]. Unique links are assigned each participant at
198 enrollment.

199 Each day, all participants receive daily messages. Participants will be asked to rank 8
200 core values based on personal importance (i.e., politics, religion, family and friends, creativity,
201 money, independence, humor, and spontaneity) during baseline assessment (T1). Participants in
202 the intervention group receive daily prompts to reflect on their highest-ranked core value vividly
203 (e.g., think of a time when you are inspired by your family) followed by a gain-framed message
204 about being physically active (e.g., walking is good for your health). The control group will
205 receive daily prompts to reflect on an everyday activity (e.g., think of a time when you charge
206 your phone) as well as the same content of daily messages but in a loss-framed way (e.g., being
207 sedentary is harmful to your health). These daily self-affirmation and health messages will
208 consist of a combination of the same messages used in the fMRI tasks and novel messages. The
209 Walk-BEST Workbook, a guideline to improve walking safely and effectively
210 (<https://physiobiometrics.com/>), has been used as a reference source of health messages. At the
211 same time, participants will be tested on their memory for health messages from the fMRI task.
212 The participant will then rate their mood and confidence in implementing the health tips, the goal
213 of which is to examine the changing of well-being and self-efficacy of physical activity

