272 server, a cloud-based system that sends and receives hash-encrypted links. Collected anonymized
273 data are stored on the messaging site behind an administrative login on the Heroku server.

274

275 *Analysis plan*

276

277 Power calculations were performed to statistically determine the target sample size of
278 N=80 for this pilot study. The power is calculated in R based on a two-sample T-test model with
279 our primary outcome, the percent of daily sedentary time assessed using an activPAL. We
280 expected a similar baseline sedentary sample to the study by Falk et al., where participants were
281 sedentary an average of $50.6\% \pm 14.0\%$ of their time [11]. Our proposed sample size of 80
282 participants (40 per group) will allow us to detect a minimum detectable difference of 10.0%
283 between the two groups (i.e., the group difference in averaged sedentary time/total valid awake
284 time) at week 4 post intervention with a common standard deviation of 14.0% with 80% power
285 and a two-sided alpha of 0.05, with 20% drop-out rate accounted. We expect that the ratio of
286 sedentary time/total valid awake time in the self-affirmation + positive framing group will be
287 10.0% less than the control negative framing group, based on our power analysis.

288 After compiling all data across the 3 different data servers, data will be checked for
289 completeness and correctness using frequency distributions (for missing data and out-of-range
290 values). Group differences at baseline are examined for variables including demographic factors
291 (i.e., age, sex, educational level, socioeconomic status, race/ethnicity), baseline sedentary time,
292 self-report sitting time, in order to detect potential confounding factors. For the primary
293 hypothesis that self-affirmation + gain-framed messages decrease sedentary time more so than
294 loss-framed messages, and the secondary outcome of increased MVPA after the intervention, all
295 outcome measures about sedentary behavior and MVPA are first quantified using available
296 software. Changes in sedentary behavior (% daily sitting and lying time, minutes/per day in

297 physical activity) over time (3 time points) are analyzed using linear mixed effect models to
298 account for the correlated data and likely heterogeneous variability. These models will include a
299 random intercept and slope to account for subject-specific changes as well as a group (2) x time

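### Randomisation is stratified by optional MRI, and the scanner task itself delivers intervention content, but the primary model does not name the stratum and the content of the home alternative is not stated.

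*Protocol*

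**What the plan says.** MRI is optional. The SAP (Study design) responds to this in the allocation: "Therefore, we stratify the randomization by MRI participation (yes/no) to ensure the same" distribution of scanned and behavioural-only participants in the two arms.

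The scanner session is not a neutral measurement. Under Neuroimaging, the Protocol has intervention participants reflect on their top-ranked value and then see gain-framed messages, while controls reflect on their lowest-ranked value and then see loss-framed messages. The daily programme in the Protocol is made of the same ingredients and is described as "a combination of the same 21 messages the participants had seen in the fMRI scanner task mixed with 21 new messages".

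On who receives the scanner task, the Protocol gives two accounts in the same section. At Yellow Visit 2, "participants will either undergo neuroimaging (i.e., task fMRI, resting-state MRI, structural MRI, DWI) or complete replacement tasks at home". Shortly afterwards: "All participants will perform an fMRI task with a block design containing a self-affirmation manipulation". For the second session the Protocol's follow-up text says: "After the intervention, participants opting into the MRIs will undergo repeat neuroimaging (i.e., resting state MRI, structural MRI, task fMRI, DWI". It mentions no home alternative at that point.

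The SAP (Daily messaging) adds, without restriction to scanned participants, that at the "same time, participants will be tested on their memory for health messages from the fMRI task".

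The primary model (SAP, Analysis plan) has a "random intercept and slope to account for subject-specific changes as well as a group (2) x time" fixed-effect interaction, plus potential confounding covariates that are not listed for the model. The variables to be compared at baseline are demographics, baseline sedentary time and self-reported sitting. MRI status is not among them.

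**The concern.** Participants who opt into MRI receive two sessions that carry the arm-specific content. For the others, the text does not say whether the home tasks carry it at the first time point, and it describes no equivalent at the second. The trial may therefore deliver two packages, messages with scanner sessions and messages without, and the primary estimate averages them with weights set by whoever opts in. A reader who wants to know whether remote messaging works by itself could not tell from that average.

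The design treats MRI participation as important enough to stratify on, and the analysis then does not name it. If the two strata change differently over time, that difference goes into the error of the group-by-time test.

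A smaller matter is the old/new message judgement. It presupposes that everyone saw the scanner messages beforehand.

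**Working it through.** **The plan's own sample size.** Inputs from the SAP, Analysis plan: difference 10.0 percentage points, SD 14.0, two-sided alpha 0.05, power 80%, 20% drop-out, two-sample t-test. The noncentral t calculation gives n = 31.76, so 32 per arm; 32/(1 − 0.20) = 40 per arm, N = 80. Power with 32 completers per arm is 80.3%. The stated figure reproduces. It contains no stratum term and no allowance for two delivery packages.

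**Does leaving out the stratum bias the group effect?** No. Allocation is 1:1 within each stratum, so the scanned share is expected to be the same in both arms.

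**Does it cost precision?** Write the outcome as Y(it) = group and time terms + γS(i) + subject effects + error, where S is MRI stratum. In the change Y(i3) − Y(i1), the stable term γS(i) cancels, and in the mixed model the random intercept takes it up. A constant stratum difference therefore costs essentially nothing for the group-by-time contrast. If the strata differ in change by d, with opt-in share f, the variance of change contains an extra f(1 − f)d². That part is removed only by a stratum-by-time term. The documents give neither d, nor f, nor the SD of change, so no standard-error figure can be given.

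**How far could the average depend on the opt-in mix?** Assume, for illustration, that the effect is 10 points with scanner sessions and a fraction r of that without. Then the pooled effect is 10 × [f + (1 − f)r]. Power is for 32 completers per arm and SD 14.

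| Opt-in share f | r = 1 | r = 0.75 | r = 0.5 | r = 0 |
|---|---|---|---|---|
| 25% | 10.0 (80%) | 8.1 (63%) | 6.25 (42%) | 2.5 (11%) |
| 50% | 10.0 (80%) | 8.75 (69%) | 7.5 (56%) | 5.0 (29%) |
| 75% | 10.0 (80%) | 9.4 (75%) | 8.75 (69%) | 7.5 (56%) |

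Both f and r are assumptions. If the 10 points belong to messaging alone and scanning adds to it, the pooled effect would exceed 10.

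**What can be learned by stratum?** With 64 completers and f = 50% there are 16 per arm per stratum. On the SAP's SD the standard error of a within-stratum group difference is 14 × √(2/16) = 4.95, a 95% half-width of 1.96 × 4.95 = 9.7 points. With f = 25% the smaller stratum has 8 per arm: 14 × √(2/8) = 7.0, half-width 13.7. For the difference between the two stratum effects, SE = 14 × √[2/(32f) + 2/(32(1 − f))] = 7.0 at f = 50% and 8.08 at f = 25% or 75%. The difference detectable with 80% power is 2.80 × SE, that is 19.6 or 22.6 points. These use the cross-sectional SD; the SD of change is not given.

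**Memory items.** 21/(21 + 21) = 50% of the Protocol's messages count as previously seen. If, and only if, the home tasks leave them out, an unscanned participant who correctly calls every message new would score 50%.

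**Timing of the repeat scan.** The Protocol's follow-up text and the SAP's Study design place it after the intervention. The Protocol's schedule, whose layout is damaged, appears to put the optional MRI with Visit 3 and the devices in the following column. The SAP puts T3 at the start of the last intervention week (Study timeline) and the devices between T3 and T4 (Physical activity monitoring). The second set would place the scan before the last device week; the first would not.

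**The case against.** Several stronger readings are tempting, and the documents do not support them.

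- *The group comparison is biased.* It is not: stratified 1:1 allocation balances scanner exposure, and both arms have an arm-specific scanner task.
- *Omitting the stratum inflates the standard error by a stated percentage.* Such a figure would describe a cross-sectional comparison with an assumed stratum gap. A stable gap cancels from the planned contrast.
- *The memory key is wrong for unscanned participants.* This depends on what the home tasks show. The Protocol shows the core values to everyone, and its wording about the 21 messages and about the fMRI task speaks of participants generally. Details may lie in attachments or figures not reproduced in the public text. Memory is rationale in the SAP Introduction, not a listed primary or secondary outcome, and the Analysis plan contains no memory analysis.
- *A second dose is given just before the outcome week.* The passages on timing disagree, so this is possible but not established.

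It can also be said that the covariate clause would admit the stratum, and that a Stage I pilot cannot resolve effects by stratum. The second stands: the detectable difference of about 20 points is twice the planned effect. The first helps little. The stratum is not named, and because it is balanced by design, a search for baseline confounders would not be expected to select it.

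**Conclusion.** The point holds as one of prespecification and interpretation. The randomisation uses MRI status, MRI status is tied to a difference in how the intervention is delivered, and the primary model does not name it. The pooled estimate is unbiased for the mix that enrols, but that mix is not stated, and any stratum difference in change is left in the error.

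The size cannot be fixed from the documents. The table shows that the consequence ranges from nothing (same effect in both strata) to a large loss of power (no effect without scanning), under assumed opt-in shares of 25% to 75%. These are conditions, not forecasts, and adding the stratum to the model would not restore that power. A reader might also infer that results by stratum would isolate the contribution of scanning. They would not, because participants choose whether to be scanned.

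Separately, the Protocol's two statements about who performs the fMRI task cannot both be right, and the passages on the timing of the repeat scan must be reconciled.

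**What to change.** 1. In the SAP, name MRI stratum and stratum by time as prespecified fixed effects in the primary mixed model. With three time points this uses one plus two degrees of freedom.
2. Report the group effect on change within each stratum, with confidence intervals, from a group by stratum by time model. A stratum-by-time term alone cannot show whether the group effect differs by stratum. Label the results descriptive, do not test the interaction, and note that MRI status is self-selected. Report the opt-in share.
3. In the Protocol, reconcile the sentence that has everyone performing the fMRI task with the passages that make MRI optional. State, for both time points, whether the home replacement tasks present the same prompts and the same 21 messages.
4. If they do not, limit any old/new memory analysis to the MRI stratum and describe it as a process measure.
5. Reconcile where the repeat scan falls relative to the last device week.

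The cost is SAP and Protocol wording, two model terms and one descriptive table. No additional participants or visits are needed.
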